6.1 Sponsor-Investigator Reporting Requirements – Washington University

Phase 1A: Washington University

6.1.1 Reporting to the Human Research Protection Office (HRPO) at Washington University

Reporting will be conducted in accordance with Washington University IRB Policies.

Pre-approval of all protocol exceptions must be obtained prior to implementing the change.

6.1.2 Reporting to the Quality Assurance and Safety Monitoring Committee (QASMC) at Washington University

The Sponsor Investigator (or designee) is required to notify QASMC of any unanticipated problems involving risks to participants or others occurring at WU or an BJH or SLCH institution that have been reported to and acknowledged by HRPO. (Unanticipated problems reported to HRPO and withdrawn during the review process need not be reported to QASMC.)

QASMC must be notified within **10 days** of receipt of IRB acknowledgement via email to [contact]. Submission to QASMC must include the myIRB form and any supporting documentation sent with the form.

6.1.3 Reporting to the FDA

The conduct of the study will comply with all FDA safety reporting requirements. **PLEASE NOTE THAT REPORTING REQUIREMENTS FOR THE FDA DIFFER FROM REPORTING REQUIREMENTS FOR HRPO/QASMC.** It is the responsibility of the investigator to report any unanticipated problem to the FDA as follows:

- Report any unexpected fatal or life-threatening suspected adverse reaction (refer to Appendix A for definitions) no later than **7 calendar days** after initial receipt of the information.
- Report a suspected adverse reaction that is both serious and unexpected (SUSAR, refer to Appendix A), no later than **15 calendar days** after it is determined that the information qualifies for reporting. Report an adverse event (refer to Appendix A) as a suspected adverse reaction only if there is evidence to suggest a causal relationship between the drug and the adverse event, such as:
 - A single occurrence of an event that is uncommon and known to be strongly associated with drug exposure
 - One or more occurrences of an event that is not commonly associated with drug exposure but is otherwise uncommon in the population exposed to the drug
 - An aggregate analysis of specific events observed in a clinical trial that indicates those events occur more frequently in the drug treatment group than in a concurrent or historical control group
- Report any findings from epidemiological studies, pooled analysis of multiple studies, or clinical studies that suggest a significant risk in humans exposed to the drug no later than **15 calendar days** after it is determined that the information qualifies for reporting.
- Report any findings from animal or in vitro testing that suggest significant risk in humans exposed to the drug no later than 15 calendar days after it is determined that the information qualifies for reporting.
- Report any clinically important increase in the rate of a serious suspected adverse reaction of that listed in the protocol or IB within 15 calendar days after it is determined that the information qualifies for reporting.

Submit each report as an IND safety report in a narrative format or on FDA Form 3500A or in an electronic format that FDA can process, review, and archive. Study teams must notify the Siteman Cancer Center Protocol Development team of each potentially reportable event within 1 business day after initial receipt of the information, and must bring the signed 1571 and FDA Form 3500A to the Siteman

Cancer Center Protocol Development team no later than 1 business day prior to the due date for reporting to the FDA.

Each notification to FDA must bear prominent identification of its contents (“IND Safety Report”) and must be transmitted to the review division in the Center for Drug Evaluation and Research (CDER) or in the Center for Biologics Evaluation and Research (CBER) that has responsibility for review of the IND. Relevant follow-up information to an IND safety report must be submitted as soon as the information is available and must be identified as such (“Follow-up IND Safety Report”).

6.2 Sponsor-Investigator Reporting Requirements – UT Southwestern

Phase 1B and Phase 2:

6.2.1 Reporting to the Human Research Protection Program office (HRPP) at UT Southwestern Medical Center

Reporting will be conducted in accordance with UT Southwestern Medical Center IRB Policies.

Pre-approval of all protocol exceptions must be obtained prior to implementing the change.

6.2.2 Reporting to the Data and Safety Monitoring Committee (DSMC) at UT Southwestern Medical Center

For local patients, in addition to the sponsor monitoring, the Simmons Comprehensive Cancer Data Safety and Monitoring Committee (DSMC) will be monitoring only local unanticipated SAE's as reported to the IRB. The chair will review only local unanticipated SAE's in real time. These are then reviewed quarterly at DSMC meetings. The chairman of the DSMC is responsible for this ongoing monitoring. Monitoring of serious adverse events happens by the DSMC chairman in real time and an annual review takes place to look at trends in adverse events, accrual and other applicable study events. The Principal Investigator (or a designated co-investigator) will be primarily responsible for monitoring study accrual rate, study attrition/withdrawals/dropouts, patterns of adverse events and/or unanticipated event and patterns of protocol violations and/or deviations at this site.

Trial monitoring will be conducted no less than annually and refers to a regular interval review of trial related activity and documentation which includes but is not limited to accuracy of case report forms, protocol compliance, timeliness and accuracy of Velos entries and AE/SAE management and reporting. Documentation of trial monitoring will be maintained along with other protocol related documents and will be reviewed during internal audit.

The Sponsor Investigator (or designee) is required to notify DSMC of any unanticipated problems involving risks to participants or others occurring at UTSW that have been reported to and acknowledged by HRPP. (Unanticipated problems reported to HRPP and withdrawn during the review process need not be reported to DSMC.)

DSMC must be notified in real-time as they are reported to the IRB to the UTSW Simmons Cancer Center DSMC Coordinator.

6.2.3 Reporting to the FDA

The conduct of the study will comply with all FDA safety reporting requirements. **PLEASE NOTE THAT REPORTING REQUIREMENTS FOR THE FDA DIFFER FROM REPORTING REQUIREMENTS FOR HRPP/DSMC.** It is the responsibility of the investigator to report any unanticipated problem to the FDA as follows:

- Report any unexpected fatal or life-threatening suspected adverse reaction (refer to Appendix A for definitions) no later than **7 calendar days** after initial receipt of the information.
- Report a suspected adverse reaction that is both serious and unexpected (SUSAR, refer to Appendix A), no later than **15 calendar days** after it is determined that the information qualifies for reporting. Report an adverse event (refer to Appendix A) as a suspected adverse reaction only if there is evidence to suggest a causal relationship between the drug and the adverse event, such as:
 - A single occurrence of an event that is uncommon and known to be strongly associated with drug exposure
 - One or more occurrences of an event that is not commonly associated with drug exposure but is otherwise uncommon in the population exposed to the drug
 - An aggregate analysis of specific events observed in a clinical trial that indicates those events occur more frequently in the drug treatment group than in a concurrent or historical control group
- Report any findings from epidemiological studies, pooled analysis of multiple studies, or clinical studies that suggest a significant risk in humans exposed to the drug no later than **15 calendar days** after it is determined that the information qualifies for reporting.
- Report any findings from animal or in vitro testing that suggest significant risk in humans exposed to the drug no later than 15 calendar days after it is determined that the information qualifies for reporting.
- Report any clinically important increase in the rate of a serious suspected adverse reaction of that listed in the protocol or IB within 15 calendar days after it is determined that the information qualifies for reporting.

Submit each report as an IND safety report in a narrative format or on FDA Form 3500A or in an electronic format that FDA can process, review, and archive. Study teams must notify the Department of Surgery Research team or Simmons Cancer Center team of each potentially reportable event within 1 business day after initial receipt of the information, and must bring the signed 1571 and FDA Form 3500A to the Department of Surgery Research team or Simmons Cancer Center team no later than 1 business day prior to the due date for reporting to the FDA.

Each notification to FDA must bear prominent identification of its contents (“IND Safety Report”) and must be transmitted to the review division in the Center for Drug Evaluation and Research (CDER) or in the Center for Biologics Evaluation and Research (CBER) that has responsibility for review of the IND. Relevant follow-up information to an IND safety report must be submitted as soon as the information is available and must be identified as such (“Follow-up IND Safety Report”).

6.3 Exceptions to Expedited Reporting – Washington University and UT Southwestern

Events that do not require expedited reporting as described in Section 6.1 include:

- planned hospitalizations
- hospitalizations < 24 hours
- respite care
- events related to disease progression

Events that do not require expedited reporting must still be captured in the EDC.

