5.4.3 Electrocardiograms (ECGs)

A standard 12-lead ECG will be obtained on all subjects at baseline (within 30 minutes prior to injection of LS301), 5-10 minutes post injection, and prior to discharge at 60 minutes.

The following table lists criteria for normal limits and clinically notable limits for ECGs in adults.

ECG Variables	Normal Limits (msec)		Notable Limits (msec)	
	Low	High	Low	High
PR interval	120	200	<120	>200
QRS interval	50	100	< 50	>100
RR interval	600	1000	<600	>1000
QT interval	No lower limit	≥ 460	No lower limit	≥ 460

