10.0 APPENDIX A: Definitions for Adverse Event Reporting

A. Adverse Events (AEs)

As defined in 21 CFR 312.32:

Definition: any untoward medical occurrence associated with the use of a drug in humans, whether or not considered drug-related.

Grading: the descriptions and grading scales found in the revised NCI Common Terminology Criteria for Adverse Events (CTCAE) version 5.0 will be utilized for all toxicity reporting. A copy of the CTCAE version 5.0 can be downloaded from the CTEP website.

Attribution (relatedness), Expectedness, and Seriousness: the definitions for the terms listed that should be used are those provided by the Department of Health and Human Services' Office for Human Research Protections (OHRP). A copy of this guidance can be found on OHRP's website:

<http://www.hhs.gov/ohrp/policy/advevntguid.html>

B. Suspected Adverse Reaction (SAR)

As defined in 21 CFR 312.32:

Definition: any adverse event for which there is a reasonable possibility that the drug caused the adverse event. "Reasonable possibility" means there is evidence to suggest a causal relationship between the drug and the adverse event. "Suspected adverse reaction" implies a lesser degree of certainty about causality than adverse reaction, which means any adverse event caused by a drug.

C. Life-Threatening Adverse Event / Life Threatening Suspected Adverse Reaction

As defined in 21 CFR 312.32:

Definition: any adverse drug event or suspected adverse reaction is considered "life-threatening" if, in the view of the investigator, its occurrence places the patient at immediate risk of death. It does not include an adverse event or suspected adverse reaction that, had it occurred in a more severe form, might have caused death.

D. Serious Adverse Event (SAE) or Serious Suspected Adverse Reaction

As defined in 21 CFR 312.32:

Definition: an adverse event or suspected adverse reaction is considered "serious" if, in the view of the investigator, it results in any of the following outcomes:

- Death
- A life-threatening adverse event
- Inpatient hospitalization or prolongation of existing hospitalization
- A persistent or significant incapacity or substantial disruption of the ability to conduct normal life functions
- A congenital anomaly/birth defect

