11.0 APPENDIX B: Reporting Timelines

Event	HRPO – Washington University	HRPPO – UT Southwestern	QASMC – Washington University	DSMC – UT Southwestern	Expedited Reporting Timelines
					FDA
Serious AND unexpected suspected adverse reaction				Submit SAE Report to SCCC DSMC within 5 business days of study team awareness of the event(s)	Report no later than 15 calendar days after it is determined that the information qualifies for reporting
Unexpected fatal or life-threatening suspected adverse reaction				Submit within 5 business days of study team awareness of the event(s)	Report no later than 7 calendar days after initial receipt of the information
Unanticipated problem involving risk to participants or others	Report within 10 working days. If the event results in the death of a participant enrolled at WU/BJH/SLCH, report within 1 working day.	Submit within 5 business days of study team awareness of the event(s)	Report via email after IRB acknowledgment	Submit UPIRSO Report to SCCC DSMC within 5 business days of study team awareness of the event(s)	
Major deviation	Report within 10 working days. If the event results in the death of a participant enrolled at WU/BJH/SLCH, report within 1 working day.	Submit within 5 business days of study team awareness of the event(s)			Report no later than 15 calendar days after it is determined that the information qualifies for reporting

Event	Expedited Reporting Timelines				
	HRPO – Washington University	HRPPO – UT Southwestern	QASMC – Washington University	DSMC – UT Southwestern	FDA
A series of minor deviations that are being reported as a continuing noncompliance	Report within 10 working days.	Submit within 5 business days of study team awareness of the event(s)			
Protocol exception	Approval must be obtained prior to implementing the change	Approval must be obtained prior to implementing the change			
Clinically important increase in the rate of a serious suspected adverse reaction of that list in the protocol or IB					Report no later than 15 calendar days after it is determined that the information qualifies for reporting
Complaints	If the complaint reveals an unanticipated problem involving risks to participants or others OR noncompliance, report within 10 working days. If the event results in the death of a participant enrolled at WU/BJH/SLCH, report within 1 working day. Otherwise, report at the time of continuing review.	Submit within 5 business days of study team awareness of the event(s)			

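### Section 6.3 exempts hospital stays under 24 hours from expedited reporting without regard to relatedness, which conflicts with the 15-day FDA rule for serious, unexpected suspected reactions to LS301

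*Combined protocol and SAP*

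**What the plan says.** Section 6.3 opens its list with "Events that do not require expedited reporting as described in Section 6.1 include" and includes "hospitalizations < 24 hours" beside planned admissions, respite care and disease-progression events. No item is limited by cause, relatedness to LS301 or expectedness. Exempt events must still be entered in the EDC.

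Appendix A, in its definition of a serious adverse event, lists "Inpatient hospitalization or prolongation of existing hospitalization" with no minimum stay.

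Section 6.1.3 (Washington University, phase 1A) gives the FDA rule: "Report a suspected adverse reaction that is both serious and unexpected (SUSAR, refer to Appendix A), no later than" 15 calendar days. Section 6.2.3 repeats it for UT Southwestern (phases 1B and 2). The FDA column of the expedited table in Appendix B agrees: "Report no later than 15 calendar days after it is determined that the information qualifies for reporting". None of these three places makes an exception for short stays.

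The routine table in Appendix B sends a serious event that does not need expedited reporting to the FDA in the toxicity table that accompanies the IND annual report.

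Sections 6.1.3 and 6.2.3 also promise compliance with all FDA safety reporting rules. Section 6.3 neither repeats that promise nor makes itself subject to it.

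**The concern.** LS301 is given once, by a 5-10 minute injection in an office or pre-operative room (Section 5.2.3). The last ECG is taken "prior to discharge at 60 minutes" (Section 5.4.3), and surgery follows 4-24 hours after the injection. In that setting, an acute reaction that leads to a brief admission is a plausible form of serious event, and the short-stay exemption falls directly on it.

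This is the first use of LS301 in humans, so an unexpected serious reaction is the kind of event that expedited reporting exists to bring forward. What is at stake is whether such a reaction reaches the FDA by the 15-day route or by a routine periodic one. A coordinator who looks for exceptions will find a specific one in 6.3 and nothing there to say that it yields to 6.1.3 or 6.2.3.

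**Working it through.** The documents give no rate, sample size or test that bears on this point, so the check is a comparison of passages.

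**Test event.** Take an unexpected reaction, suspected to be due to LS301, that leads to an inpatient stay of 12 hours. The 12 hours is illustrative; any inpatient stay under 24 hours gives the same result.

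| Question | Source | Answer for the test event |
|---|---|---|
| Is it serious? | Appendix A, definition of a serious event | Yes: inpatient hospitalization, no minimum stay |
| Is it due to the FDA? | 6.1.3 (phase 1A), 6.2.3 (phases 1B and 2) | Yes: serious, unexpected and suspected, so 15 calendar days |
| Does the timeline grid make an exception? | Appendix B, expedited table | No |
| Is it exempt? | 6.3 | Yes: under 24 hours, no condition on cause |
| What then happens? | 6.3; Appendix B, routine table | EDC entry; to the FDA with the IND annual report |

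The second and fourth rows cannot both be followed.

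**Which events are affected.** All of these must hold: the stay is under 24 hours; it is an inpatient admission; the reaction is suspected to be caused by LS301; and it is unexpected. A short stay that is not an inpatient admission does not meet the Appendix A hospitalization criterion, but 6.3 does not draw that line. The conflict is sharpest when the admission is the only reason the event is serious.

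**Which sites are affected.** The heading "6.3 Exceptions to Expedited Reporting – Washington University and UT Southwestern" names both sites, but the operative sentence cites Section 6.1 alone, and UT Southwestern's FDA rules are in 6.2.3. For phase 1A the conflict is explicit. For phases 1B and 2 it rests on the heading. Section 6.0 does not settle the scope, because it sends FDA reporting to a Section 6.4 that is absent from the current text.

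**The case against.** The strongest reply is that 6.3 is not a waiver. Sections 6.1.3 and 6.2.3 commit to every FDA safety reporting rule and warn in capitals that FDA requirements differ from local ones, and Appendix B has no short-stay exception. A careful team could read 6.3 as excusing the stay itself and not the reaction behind it, particularly since Appendix A also makes life-threatening and other important medical events serious on their own grounds. This stands in part: the documents conflict and do not plainly direct non-reporting. But nothing says which passage prevails.

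Three stronger readings are tempting, and the documents do not support them.

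- *Further cohorts would be dosed because of 6.3.* Under 5.2.1.1, escalation may proceed once the last patient in a cohort completes one hour of monitoring, so a 15-day FDA report would not hold it back even if 6.3 were deleted. Escalation is governed by the dose-limiting toxicity rule in 5.2.1.3 and 8.1, which 6.3 does not touch.
- *All oversight is delayed until a periodic review.* Sections 7.1 and 7.2 require ongoing monitoring of serious toxicities and reporting of adverse events to local bodies under institutional guidelines. At UT Southwestern the monitoring committee chair reviews local unanticipated serious events in real time (6.2.2). Appendix B sets 5 business days for that committee, and for unanticipated problems 10 working days for the Washington University review office. Some of these deadlines are themselves expedited items that a reader might think 6.3 reaches, but Section 7 stands apart from it. The FDA also reviews the phase 1 data before phase 2 opens. The delay that can be shown is the one to the FDA.
- *Every short admission is a missed report.* Only reactions that are both suspected and unexpected fall under the 15-day rule.

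A reader might also infer that 6.3 cancels the 7-day report for an unexpected life-threatening reaction with a short stay. The wording does not exclude this, but such an event is serious without the hospitalization criterion, so the point does not rest on it.

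**Conclusion.** The conflict is real. For a short inpatient admission caused by an unexpected suspected reaction to LS301, Appendix A with 6.1.3, 6.2.3 and Appendix B calls for an FDA report within 15 calendar days, while 6.3 excuses it. If 6.3 governs, the scheduled FDA route is the IND annual report.

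The size is a matter of reporting route and not of frequency: the documents give no event rate, and dividing one assumed event by the planned enrolment would not supply one. The affected events are probably few.

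The conclusion assumes that 6.3 is applied as worded and that the stay is a true inpatient admission. For phases 1B and 2 it also assumes that the heading of 6.3 extends its text to Section 6.2. It does not assume that the sponsor intends to withhold such reports. The passages should be reconciled. The change merits making because the error would fall on a reportable safety event in a first-in-human study and the correction is small.

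**What to change.** Add a sentence to 6.3 stating that its exceptions do not apply to suspected adverse reactions to LS301, which follow 6.1.3 or 6.2.3 and Appendix B whatever the length of stay.

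With that limit in place, cite Section 6.2 as well as 6.1, so that text and heading agree for both sites. The order matters: adding 6.2 without the limit would widen the exemption to phases 1B and 2. The reference in Section 6.0 to a missing Section 6.4 can be corrected in the same edit, to point to 6.1.3 and 6.2.3.

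The cost is about one sentence and two cross-references, with possibly a few more expedited reports. Dosing, escalation and analysis are unchanged.

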7.0 DATA AND SAFETY MONITORING

7.1 Phase 1A: Washington University

In compliance with the Washington University Institutional Data and Safety Monitoring Plan, the Principal Investigator will provide a Data and Safety Monitoring (DSM) report to the Washington University Quality Assurance and Safety Monitoring Committee (QASMC) semi-annually beginning six months after accrual has opened (if at least one patient has been enrolled) or one year after accrual has opened (if no patients have been enrolled at the six-month mark).

The Principal Investigator will review all patient data at least every 6 months, and provide a semi-annual report to the QASMC. This report will include:

- HRPO protocol number, protocol title, Principal Investigator name, data coordinator name, regulatory coordinator name, and statistician name
- Date of initial HRPO approval, date of most recent consent HRPO approval/revision, date of HRPO expiration, date of most recent QA audit, study status, and phase of study

- History of study including summary of substantive amendments; summary of accrual suspensions including start/stop dates and reason; and summary of protocol exceptions, error, or breach of confidentiality including start/stop dates and reason
- Study-wide target accrual and study-wide actual accrual
- Protocol activation date
- Average rate of accrual observed in year 1, year 2, and subsequent years
- Expected accrual end date and accrual by cohort
- Objectives of protocol with supporting data and list the number of participants who have met each objective
- Early stopping rules with supporting data and list the number of participants who have met the early stopping rules
- Summary of toxicities separated by cohorts with the number of dose-limiting toxicities indicated
- Abstract submissions/publications
- Summary of any recent literature that may affect the safety or ethics of the study

The study principal investigator and Research Patient Coordinator will monitor for serious toxicities on an ongoing basis. Once the principal investigator or Research Patient Coordinator becomes aware of an adverse event, the AE will be reported to the HRPO and QASMC according to institutional guidelines.

